## 4.5 Study Rationale

This study is designed to investigate, at first, safety and tolerability of a novel liquid vaccine formulation named MV-ZIKA-RSP, in healthy adults aged 18 to 55 years.

For this purpose, two different doses of MV-ZIKA-RSP ( $1 \times 10^5$  TCID50 and  $2,5 \times 10^4$  TCID50 per dose), and one group receiving only placebo, will be assessed in healthy adults for one or two immunizations and at different time points.

The induction of functional anti-zika-rsp antibodies by MV-ZIKA-RSP will be investigated, by means of immunoassays like VNT and supported with assays like ELISA and T-cell analysis. In our previous clinical studies, it is demonstrated that the timepoints day 28 and day 56, after immunisation, are suitable for elicitation of immunogenicity.

The different vaccination schedules:

- two MV-ZIKA-RSP vaccinations (high dose) on days 0 and 28
- two MV-ZIKA-RSP vaccination (low dose) on day 0 and 28
- one MV-ZIKA-RSP vaccination (high dose) on day 0 and placebo on day 28
- two placebo injections on day 0 and 28

will allow us a comparison between immunogenicity of these dosing regimens. A single shot or two vaccinations within a short period of time are desirable to allow for a quick immunisation before travelling to areas with active transmission of the zika virus and at the same time will reveal valuable information on future treatment recommendations (single shot treatment vs. double immunisation).

With a design of randomised, observer-blinded study we will be able to record and assess all adverse events.

Since the induction of virus specific T cells is a critical step in the generation of a functional immune response, the rate of zika virus specific T cells will be analysed *in vitro*.

This study was designed according to the Note for Guidance on Clinical Evaluation of New Vaccines (CHMP/VWP/164653/2005), and will be conducted in compliance with the protocol, Good Clinical Practice (GCP) as set forth in the International Council on Harmonisation (ICH) guidelines on GCP (ICH E6), and applicable local regulatory requirements.

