***Please note:***

*As this is a first in humans' study, the site should initially enroll a group of six participants and then pause with enrollment until these participants completed their Post Dose Safety Follow Up one week after the first vaccination. If no events as defined in section 8.9.1 "Safety Stopping Rule" are identified, the site should resume enrolling participants. If such events were identified, the investigators and the sponsor need to assess the risk of continuing the study and based on this assessment to decide if or if not, the study should be continued.*

The 48 participants will be distributed between the 4 groups using a randomisation ratio of 14 : 14 : 12 : 8 = A : B : C : D, with an adequate representation of high dose, low dose and placebo subjects (2 : 2 : 0 : 2 = A : B : C : D) within the first 6 subjects to allow for the safety evaluation after the first vaccination.

A subject will be considered enrolled once the first IMP administration has been performed according to randomisation.

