### 12.2 Methods of Statistical Immunogenicity Analysis

The immunogenicity analysis will compare the anti-zika-rsp VNT antibody geometric mean titre (GMT) in the Per Protocol (PP) analysis population between the treatment groups. GMTs and GMT ratios will be estimated by applying an analysis of variance including the factor treatment group. This will be done using  $\log_{10}$  transformed data and taking the anti-log of the resulting point estimates for the least squares means, least squares means differences and the corresponding 2-sided 95% CIs.

P-values will also be provided to compare GMTs between the treatment groups adjusted for multiple comparisons according to Tukey-Kramer. Seroconversion rates will be compared between groups using Fisher's exact test.

Seroconversion will be defined as anti-zika-rsp VNT titres  $\geq 20$ .

ZIKA-RSP- and measles- ELISA titres will be analysed as described above.

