## 2.6 Inferential Analyses

The analysis for primary endpoint will compare adverse events rates up to day 56 between treatment groups using Fisher-Freeman-Halton test. The same overall test between treatment groups will be performed for all adverse event tables in the Day 56 analysis as well as the final analysis.

The immunogenicity analysis will compare the anti-zika-rsp VNT antibody geometric mean titer (GMT) in the Per Protocol (PP) analysis population between the treatment groups. GMTs and GMT ratios will be estimated by applying an analysis of variance including the factor treatment group. This will be done using log10 transformed data and taking the anti-log of the resulting point estimates for the least squares means, least squares means differences and the corresponding 2-sided 95% CIs.

P-values will also be provided to compare GMTs between the treatment groups adjusted for multiple comparisons according to Tukey-Kramer.

For the primary immunogenicity analysis, values below the lower limit of detection are replaced by half of the limit and values above the upper limit are replaced by the upper limit.

As sensitivity analysis, an analysis of immunogenicity will be applied, that does not use such imputation. Therefore, observations will be interval-censored and GMTs will be estimated by assuming normal distribution for the log-transformed values (intervals). Values below the lower limit of detection will be left-censored at the lower limit and values above the upper limit (if applicable) will be right-censored at the upper limit.

Seroconversion rates and positivity rates will be compared between groups using Fisher-Freeman-Halton test.

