### 5.1 Data points

The following information will be analyzed by visit descriptively in tables and corresponding details on the subject level will be provided in data listings:

- GMT of Zika-RSP VNT antibody (incl. ANOVA with fixed treatment group as described in Section 2.6)
- Seroconversion rate for Zika-RSP VNT antibody (incl. test as described in Section 2.6)
- Positive/Negative results for NT
- GMT of Zika-RSP-ELISA antibodies (incl. ANOVA with fixed treatment group)
- Seroconversion rate for Zika-RSP-ELISA antibodies
- Positive/Negative results for ZIKA ELISA
- GMT of Measles-ELISA antibodies (incl. ANOVA with fixed treatment group)
- Seroconversion rate for Measles-ELISA antibodies
- Positive/Negative results for MV ELISA
- specific functional CD4+ T-cells by visit (without geometric mean):
  - E+prM positive/negative
  - E values
  - prM values

Sampling details for VNT, ELISA Zika-RSP, ELISA measles and T-cells immunity (will be listed only)

Specifications on TLFs are provided in [Section 7](#).

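### Seroconversion and positivity rates get only a global four-group test that includes placebo, with no regimen contrast and no rate difference with a confidence interval

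*Combined protocol and SAP*

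**What the plan says.** Protocol 4.5 sets out four schedules (two high doses, two low doses, one high dose then placebo, two placebo injections) and says that they "will allow us a comparison between immunogenicity of these dosing regimens". It names single versus double immunisation as part of that question. Information on the optimal dose is a secondary objective (protocol 5.2, SAP 1.1.2).

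For response rates, protocol 12.2 says "Seroconversion rates will be compared between groups using Fisher's exact test". It does not say whether the test is overall or pairwise. SAP 2.6 settles on one form: "Seroconversion rates and positivity rates will be compared between groups using Fisher-Freeman-Halton test". For adverse events the same section uses the same test and describes it as overall: "The same overall test between treatment groups will be performed for all adverse event tables". SAP 5.1 refers back to that section: "Seroconversion rate for Zika-RSP VNT antibody (incl. test as described in Section 2.6").

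GMTs are treated differently. SAP 2.6 estimates GMT ratios with two-sided 95% intervals and adds: "P-values will also be provided to compare GMTs between the treatment groups adjusted for multiple comparisons according to Tukey-Kramer". Tables 2.3.1.4, 2.3.1.5, 2.3.1.9 and 2.3.1.10 in SAP 7.1, and their per-protocol repeats, list seroconversion and positivity with no pairwise comparison, no comparison without placebo and no rate difference.

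**The concern.** The null hypothesis of the four-group test is that A, B, C and D share one response probability. It is false once any regimen differs from saline, even if A, B and C are identical. The regimen questions are narrower: A versus B for dose, and A versus C for two doses against one. No planned test or interval on the response rates addresses either.

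What is at stake is interpretation. A small p-value printed beside four regimen rates invites the reading that the regimens differ. If response is high on every regimen, such a p-value is expected anyway. A non-significant result does not show which regimen, if any, responded.

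**Working it through.** The documents give no expected seroconversion rate, power or test level, so there is no figure of theirs to reproduce.

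**Inputs.** Group sizes are 14, 14, 12 and 8 (protocol 8.2, "using a randomisation ratio of 14 : 14 : 12 : 8 = A : B : C : D"). The assumptions are:
- two-sided 0.05, in line with the 95% intervals;
- no dropout;
- vaccine response from 30% to 90%;
- placebo response of 0%, 5% or 12.5%.

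The 12.5% is 1/8. Protocol 4.4.1 reports one placebo seroconverter in the predecessor trial. The placebo arm size of 8 follows from its solicited adverse event figures: 70.0% of 40 vaccinees is 28, plus 8 of 8 on placebo, gives the reported 36 of 48.

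**Method.** For every possible table, the exact p-value is the sum of the conditional probabilities of all tables with the same total that are no more likely than the observed one. The rejection probability is the sum, over tables with p ≤ 0.05, of the product of the four binomial probabilities.

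**Rejection probability when A = B = C (%)**

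| Vaccine rate | Four groups, placebo 0% | Four groups, placebo 5% | Four groups, placebo 12.5% | A, B, C only |
|---|---|---|---|---|
| 30% | 15.3 | 11.3 | 7.4 | 4.7 |
| 40% | 37.6 | 27.1 | 16.6 | 4.6 |
| 50% | 73.5 | 54.2 | 33.8 | 4.5 |
| 60% | 95.8 | 77.5 | 54.6 | 4.6 |
| 70% | 99.9 | 92.1 | 76.7 | 4.7 |
| 80% | 100.0 | 98.6 | 92.7 | 4.0 |
| 90% | 100.0 | 99.9 | 99.1 | 2.3 |

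At high response the four-group test rejects nearly always with no regimen difference. The same test without placebo stays below 5%.

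**Single tables (A, B, C, D)**
- 12/14, 12/14, 10/12, 0/8: four-group p = 0.00003; A, B, C only p = 1.0.
- 12/14, 9/14, 7/12, 0/8: four-group p = 0.0008; A, B, C only p = 0.32; A versus B p = 0.39; A versus C p = 0.19.
- 7/14, 7/14, 6/12, 0/8: four-group p = 0.058, so half the vaccinees respond and the test does not reject.

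**What an interval would show.** Take A 12/14 (85.7%, Wilson 60.1 to 96.0) and C 7/12 (58.3%, Wilson 32.0 to 80.7) from the second table. The difference is 27.4 points. The Newcombe limits are:
- lower: 27.4 − √(25.7² + 22.3²) = 27.4 − 34.0 = −6.6;
- upper: 27.4 + √(10.3² + 26.4²) = 27.4 + 28.3 = 55.7.

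The interval of −6.6 to 55.7 points says plainly what the four-group p of 0.0008 does not: the regimen difference is unresolved.

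**Power of regimen contrasts.** With true rates of 90%, 70% and 50%, Fisher's test has 14% power for A versus B and 56% for A versus C.

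**The case against.** The strongest reply is that this is a secondary endpoint in a Phase I trial without a formal sample size calculation, where an overall exact test beside by-group rates is a defensible exploratory choice. SAP 2.6 itself describes the test as overall when it applies it to adverse events. Rates are tabulated by group and visit, so anyone can compute a difference and interval from the counts. Regimens are compared pairwise on VNT GMT, and the dose objective rests on safety, tolerability and VNT immunogenicity together. All of this stands, and it limits the point to one part of the analysis.

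It does not remove the point. Seroconversion has its own planned p-value, and readers will interpret it. The VNT threshold of 20 is also the assay's lower limit of quantification (protocol section 20), so titres below it enter the GMT analysis at half the limit. The GMT comparison is therefore not a full substitute for the response rate.

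Three stronger readings are tempting and not supported:
- **The test rejects whenever the vaccine works at all.** A false null is not a rejection. At 30% to 50% response and 5% placebo it rejects in 11% to 54% of trials.
- **The p-value looks the same whether or not regimens differ.** With 90/50/50% and placebo 5%, the test rejects in 98.5%. The mean vaccine rate is (14 × 0.9 + 26 × 0.5)/40 = 64%, and equal arms at 64% give 84%. At 60/20/20% (mean 34%) it is 72% against 16%. The test does respond to regimen differences, but it cannot attribute a rejection to them.
- **The plan cannot answer the dosing question.** By-group rates and pairwise GMT ratios both bear on it.

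**Conclusion.** The point holds in limited form. For seroconversion and positivity, the SAP plans only a global test with placebo included. It plans no regimen contrast and no rate difference with an interval. If vaccine response is about 60% or more and placebo is near 5%, that test rejects in 77.5% to 99.9% of trials with identical regimens. A significant result then mainly shows vaccine versus saline and cannot by itself support a dose or one-versus-two-dose conclusion. If placebo response is 12.5%, the range is 54.6% to 99.1%.

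At lower response the problem is different: the test often misses a real vaccine effect. These figures depend on assumed response rates, a 0.05 level and no dropout. The documents point both ways on likely response: the predecessor trial had seven vaccinee seroconverters among 40, while the macaque data and the related chikungunya vaccine suggest high rates. The omission itself does not depend on those assumptions. It is a cheap improvement to a secondary analysis and does not touch the primary safety endpoint.

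**What to change.** In SAP 2.6, and in tables 2.3.1.4, 2.3.1.5, 2.3.1.9 and 2.3.1.10 with their per-protocol repeats, add rate differences with exact or Newcombe 95% intervals for:
- each vaccine regimen versus placebo, at Days 28 and 56;
- A-B, at Days 28 and 56;
- A-C, at Day 56 only. At Day 28, A and C have each had the same single high dose, so that contrast carries no regimen information.

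Label the four-group p-value in the text and table footnotes as a global test, placebo included, that does not address differences between regimens. Further p-values are optional and should be called exploratory.

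The cost is SAP wording and table columns, with no new data. Each table gains four intervals at Day 28 and five at Day 56. Over four tables and two populations that is 9 × 4 × 2 = 72 secondary intervals, unadjusted unless the SAP says otherwise. They will be wide: two arms of 14 with 12 responders each give 0 ± 27.6 points by Newcombe (25.7 and 10.3 combined as √(25.7² + 10.3²), about 27.6). They serve to show the uncertainty and will seldom establish a difference.

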## 2.7 Center and Country Effect

Not applicable since this is a single-center study.

## 2.8 Handling Missing Data

Generally, missing values will not be imputed, and the analysis will be limited to observed values. But for missing data in the AE (e.g. missing information about seriousness, severity or causality) a worst case approach will be applied. For example, adverse events with missing severity assessments will be considered as “Potentially life threatening” and events with missing relationship to study treatment are counted as “Definitely” related to study treatment. In case of missing assignment to solicited or unsolicited, this AE will neither be counted in tables for solicited AEs nor in tables for unsolicited AEs but in tables for all AEs.

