#### Unsolicited AEs:

Separately, the number and percentage of participants with unsolicited/spontaneous adverse events (AEs) and serious adverse events (SAEs) will be presented for each treatment group overall, and by system organ class/preferred term, by AE grade, and relatedness. Fisher exact tests will be provided for a comparison of AE rates between treatment groups.

Laboratory values and vital signs as well as changes in laboratory values from baseline will be analysed descriptively by time point and treatment group.

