## 12.7 Missing Data

All attempts will be made to prevent missing data and generally, missing data will not be imputed, and analysis will be limited to observed values. However, for missing data in AE evaluation (e.g. missing information about severity or causality) a worst-case approach will be applied.

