## 6.2 Adverse Events

### 6.2.1 *Data points*

The following analyses will be provided for all Adverse Events:

- Adverse event overview for solicited and unsolicited events (e.g. any AE, any SAE, any related AE).
- Solicited Adverse Events by symptom
- Solicited Adverse Events by symptom and severity
- Unsolicited Adverse Events by SOC and PT, overall and for specific types of Adverse Events (e.g. SAEs, related AEs)
- Unsolicited Adverse Events by severity and for specific types of Adverse Events
- Unsolicited Adverse Events by causality and for specific types of Adverse Events

For details on table and listing content, see Section 7.

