| n/a  | 2.3.1.10        | Positivity of Zika-RSP-ELISA Antibodies by time point  |   |
| Measles-ELISA antibodies  |                 |  |   |
| n/a  | 2.3.1.11        | GMT of Measles-ELISA Antibodies by Visit (mITT Population)   |   |
| n/a  | 2.3.1.12        | GMT of Measles-ELISA Antibodies based on interval-censored data by Visit (mITT Population)   |   |
| n/a  | 2.3.1.13        | ANOVA for GMT Measles-ELISA Antibodies between treatment groups by Visit (mITT Population)   |   |
| n/a  | 2.3.1.14        | Seroconversion rate of Measles-ELISA Antibodies by Visit (mITT Population)   |   |
| n/a  | 2.3.1.15        | Positivity of Measles-ELISA Antibodies by time point   |   |

| T cell immunity    |                  |   |  |
|---------------------------|------------------|---|--|
| n/a                       | 2.3.1.16         | Median of SFC of T cell immunity-PBMCs by Visit (mITT Population)             |  |
| n/a                       | 2.3.1.17         | Positivity of SFC of T cell immunity-PBMCs by time point                      |  |
| n/a                       | 2.3.2.1-2.3.2.17 | Repeat Immunogenicity tables 2.3.1.1-2.3.1.17 for PP Population.              |  |
| Safety Results     |                  |   |  |
| Extent of Exposure |                  |   |  |
| 1.4.1.1                   | 2.4.1.1          | Extent of Exposure (Safety Population)  | 
 
• Study duration
 
• Treatment duration
 
   |
| Adverse Events     |                  |   |  |
| 1.4.1.2                   | 2.4.1.2          | Summary Table of solicited and unsolicited Adverse Events (Safety Population) | 
Number of subjects with:
 
 
• Any AEs
 
• Any related AEs
 
• Any severe AEs
 
• Any related severe AEs
 
• Any SAEs
 
• Any related SAEs
 
• Any medically attended AEs
 
• Any related medically attended AEs
 
• Any AEs leading to second vaccination not administered
 
   |

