| 1.4.1.6                           | 2.4.1.6  | Summary Table of unsolicited Adverse Events (Safety Population)   | 
 
• Any unsolicited AEs
 
• Any related unsolicited AEs
 
• Any severe unsolicited AEs
 
• Any serious unsolicited AEs
 
• Any medically attended unsolicited AEs
 
• Any related severe unsolicited AEs
 
• Any related serious unsolicited AEs
 
• Any related medically attended unsolicited AEs
 
• Any unsolicited AEs leading to second vaccination not administered
 
 |
| 1.4.1.7                           | 2.4.1.7  | Subjects with at least one Adverse Event classified by Maximum Severity (Safety Population)                   |  |
| Solicited Adverse Events   |          |   |  |
| 1.4.1.8                           | 2.4.1.8  | Subjects with solicited local Adverse Events by Symptom (Safety Population)                                   |  |
| 1.4.1.9                           | 2.4.1.9  | Subjects with solicited systemic Adverse Events by Symptom (Safety Population)                                |  |
| 1.4.1.10                          | 2.4.1.10 | Subjects with solicited Adverse Events classified by Maximum Severity (Safety Population)                     |  |
| 1.4.1.11                          | 2.4.1.11 | Subjects with solicited local Adverse Events by Symptom classified by Maximum Severity (Safety Population)    |  |
| 1.4.1.12                          | 2.4.1.12 | Subjects with solicited systemic Adverse Events by Symptom classified by Maximum Severity (Safety Population) |  |
| Unsolicited Adverse Events |          |   |  |
| 1.4.1.13                          | 2.4.1.13 | Subjects with unsolicited Adverse Events by PT (Safety Population)  |  |
| 1.4.1.14                          | 2.4.1.14 | Subjects with unsolicited Adverse Events by SOC and PT (Safety Population)                                    |  |
| 1.4.1.15                          | 2.4.1.15 | Subjects with related unsolicited Adverse Events by SOC and PT (Safety Population)                            |  |
| 1.4.1.16                          | 2.4.1.16 | Subjects with severe unsolicited Adverse Events by SOC and PT (Safety Population)                             |  |

|  |          |   |  |
|--|----------|---|--|
| 1.4.1.17   | 2.4.1.17 | Subjects with serious unsolicited Adverse Events by SOC and PT (Safety Population)                              |  |

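### An adverse event with no solicited/unsolicited label is left out of every table by symptom, SOC/PT or causality, at odds with the plan's worst-case rule for missing AE data

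*Combined protocol and SAP*

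**What the plan says.** Protocol 12.7 leaves missing data unimputed in general but makes an exception for adverse events: "for missing data in AE evaluation (e.g. missing information about severity or causality) a worst-case approach will be applied". SAP 2.8 repeats the exception. A missing severity goes to the top grade and a missing relationship to the strongest category. The paragraph then closes with a different rule for a missing solicited/unsolicited assignment: "this AE will neither be counted in tables for solicited AEs nor in tables for unsolicited AEs but in tables for all AEs".

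On presentation, the unsolicited-AE part of Protocol 12.3 says that "serious adverse events (SAEs) will be presented for each treatment group overall, and by system organ class/preferred term", and also by grade and relatedness. The synopsis likewise promises summaries of SAEs by severity and term.

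SAP 7.1 lists the AE tables as x.4.1.2 to x.4.1.28, where x is 1 for the preliminary and 2 for the final analysis. The serious-event table by term, x.4.1.17, is titled "Subjects with serious unsolicited Adverse Events by SOC and PT (Safety Population").

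**The concern.** Under every other stated rule for a missing AE item, the event is kept and counted on the unfavourable side. SAP 6.2.2 treats missing causality as related, puts a missing grade into the severe tables, and places an unknown onset within the day 56 window. A missing type is the only item whose rule takes the event out of tables.

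Safety is the primary objective of this first-in-human trial. The by-term and by-causality tables are where a reader sees which events occurred in which group and how they were judged. With 8 to 14 participants per group, one missing event is visible in a percentage. SAP 2.6 also applies the between-group test to all AE tables, so the tests in the affected tables would run on the reduced counts.

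**Working it through.** The plan states no figure to reproduce here. The check classifies each planned AE table and listing by the events it admits.

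**Step 1. AE tables in SAP 7.1 (x.4.1.2 to x.4.1.28).**

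| Scope | Tables | Number |
|---|---|---|
| All AEs | .2, .7 | 2 |
| Solicited only | .3, .4, .5, .8 to .12 | 8 |
| Unsolicited only | .6, .13 to .28 | 17 |
| Total | | 27 |

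An unlabelled AE is absent from 8 + 17 = 25 of 27 tables.

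**Step 2. Tables that show what the event was or how it was attributed.**
- Explicitly by symptom, PT or SOC/PT: .8, .9, .11, .12 (solicited) and .13 to .21 (unsolicited), so 4 + 9 = 13. None takes all AEs.
- By causality category: .26, .27, .28. None takes all AEs.

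**Step 3. AE listings in SAP 7.2 (x.4.3 to x.4.32).** Two are unrestricted (x.4.3, x.4.4), 14 are unsolicited (x.4.5 to x.4.18) and 14 are solicited (x.4.19 to x.4.32). Total 30.

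**Step 4. Follow one record: a related SAE with a blank type field.**
- Counted: the any-AE, related, SAE and related-SAE rows of x.4.1.2 (the last is "Any related SAEs"), and x.4.1.7.
- Listed: x.4.3, with PT, SOC, seriousness, SAE criteria and relationship, and x.4.4.
- Absent: related by SOC/PT (.15), serious by SOC/PT (.17), related serious by SOC/PT (.20), serious by causality (.28), and the serious-event listings x.4.11 and x.4.12.

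No table shows its term. If severity were blank as well, the worst-case rule would give it the top grade in x.4.1.7, yet it would not appear in the severe-by-SOC/PT table (.16).

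**Step 5. Largest effect of one omitted participant on a by-term rate.** SAP 6.2.2 bases AE percentages on the group total, so the shift is 100 × 1/n, taking the planned group sizes as the safety population.
- A and B: 100/14 = 7.1 points
- C: 100/12 = 8.3 points
- D: 100/8 = 12.5 points

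These are upper limits. They apply only if the participant has no other labelled event of the same term in that table.

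**Step 6. Primary endpoint.** It is the rate of AEs up to day 56, with no split by type (Protocol 6.2.1, SAP 1.3.1). An unlabelled AE still counts.

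**The case against.** A reader might infer that an unlabelled event, even an SAE, disappears from the report. The documents do not support that. The rule itself keeps the event in the all-AE tables, and x.4.1.2 has rows for related, severe, serious and related serious events. Listings x.4.3 and x.4.4 give its details without restriction by type.

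Other points against the concern:

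- **The trigger may be rare.** The field must still be blank at the database snapshot. The eCRF checks for incomplete entries and data queries (Protocol 15.4.1 and 15.4.2) and monitoring (13.1) work against this, and SAEs also travel on a separate report form (10.3). This stands. The documents give no rate, so no probability of occurrence can be put forward.
- **Solicited or unsolicited is not an ordered item, so it has no worst level.** This stands in part. Protocol 12.7 names severity and causality only as examples and does not dictate a category for type. Even so, leaving the event out of both families is hard to square with a worst-case approach.
- **Some gaps come from the table design.** A correctly labelled solicited SAE is also absent from x.4.1.17. True, but it still appears under its symptom in x.4.1.8 or x.4.1.9; an unlabelled one appears under no term in any table.
- **Protocol 12.3 names SAEs under the unsolicited heading,** so it could be read as covering unsolicited SAEs only. The synopsis lists SAEs as a separate item to be summarised by term, which favours the wider reading.

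One ambiguity cuts the other way. Table x.4.1.2 is titled "Summary Table of solicited and unsolicited Adverse Events (Safety Population"), and SAP 6.2.1 describes the overview in similar terms. Read strictly, an event that is neither type would not belong there. The plural in SAP 2.8 and the table's any-AE row make the inclusive reading the natural one, but the SAP should say so.

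**Conclusion.** The concern holds as a gap in the table rules. An AE whose label is still missing at the snapshot reaches 2 of 27 AE tables and 2 of 30 AE listings. It is absent from all 13 tables by symptom, PT or SOC/PT and all 3 by causality category, including serious and related events by SOC/PT. The by-term SAE presentation in Protocol 12.3 would be incomplete for that event, and the rule departs from the worst-case approach in Protocol 12.7 and SAP 2.8.

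The size is limited. The largest effect of one participant is 7.1 points in A or B, 8.3 in C and 12.5 in D, assuming no other event of the same term. The primary endpoint is unaffected, so it would be wrong to infer a biased primary analysis or a concealed SAE. The conclusion rests on at least one blank label surviving data cleaning, and that frequency is unknown. The case for changing the rule is that it is written down, gives incomplete safety tables whenever it applies, and costs almost nothing to replace.

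**What to change.** Replace the last sentence of SAP 2.8 with: *An AE whose label is still missing after query is counted as unsolicited in all tables, is included in x.4.1.2 and x.4.1.7, and is flagged in listing x.4.3.*

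The cost is one sentence and a few lines of code. The downside is that an occasional diary reaction would be tabulated as unsolicited; the flag makes this visible. The update note in SAP 2.1 indicates that the preliminary analysis has already been run. The new rule would then apply to the final AE tables and should be recorded as a change that does not depend on treatment group.

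Two alternatives are less attractive:

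- **Deriving the label from term and onset within the 7-day diary period.** This cannot be done reliably from the text. The systemic symptoms named for the diary in Protocol 11.7 omit diarrhoea and myalgia, which Table 6 grades, and Protocol 11.5 has solicited AEs recorded at visits up to Visit 4.
- **Adding all-AE and all-SAE tables by SOC/PT and by relatedness.** This would also bring labelled solicited SAEs into a by-term serious table, but needs several extra tables.
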